9.4. Data Sources

The US Corrona RA Registry is the data source for this study. It is an independent, prospective, national, observational cohort. Patients are recruited from 187 private and academic sites across 43 states, with 799 providers participating. Providers and subjects complete study questionnaires approximately every 6 months at routine clinic encounters. As of September 2019, the Corrona database included information on 53,438 patients with RA. Data on 403,679 patient visits and 192,141 patient-years of follow-up observation time have been collected, with a mean patient follow-up of 4.48 (median 3.24) years. Data are collected on subjects for as long as they consent to remain in the study.

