9. RESEARCH METHODS

9.1. Study Design

This is an observational study conducted in a cohort of tofacitinib-exposed patients to evaluate effectiveness of tofacitinib MR 11 mg QD tablet compared to IR 5 mg BID tablet. In this secondary data collection study of structured data, patient therapeutic strategies are not determined by this protocol.

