9.3. Variables

The US Corrona RA Registry is an efficient data collection system for evaluating a range of efficacy outcomes associated with therapies used to treat RA. The endpoints chosen for this study will be extracted from patient and physician questionnaires. Demographic data collected includes age, gender, race and ethnicity. In addition, baseline disease characteristics like disease duration and severity etc. will be captured for both the IR and MR cohorts under study to evaluate disease characteristics.

Primary outcome: Minimally clinically important difference (MCID) improvement as defined by difference in Clinical Disease activity index (CDAI) from initiation to 6 month visit. MCID is dependent on baseline disease activity (at initiation); $MCID \geq 2$ if CDAI at initiation of Low $CDAI \leq 10$, $MCID \geq 6$ if CDAI at initiation Moderate of $10 < CDAI \leq 22$ and $MCID \geq 11$ if CDAI at initiation high of > 22 .

Secondary Outcomes:

- Change in CDAI from baseline to 6 month follow-up (as a continuous variable).
- Achievement of Remission ($CDAI \leq 2.8$) at 6 month follow-up (among all).
- Achievement of Remission ($CDAI \leq 2.8$) at 6 month follow-up (among those that were not in remission at initiation).
- Achievement of Low Disease Activity (LDA) ($CDAI \leq 10$) at 6 month follow-up (among all).
- Achievement of Low Disease Activity (LDA) ($CDAI \leq 10$) at 6 month follow-up (among those that were not in remission or LDA at initiation).
- Achievement of improvement from baseline to 6 month follow-up in modified Health Assessment Questionnaire (mHAQ) of at least 0.25 (as a dichotomous variable).
- Achievement of improvement from baseline to 6 month follow-up in Health assessment questionnaire (HAQ) of at least 0.22.

- Change from baseline to 6 month follow-up HAQ (HAQ as a dichotomous variable).
- Change from baseline to 6 month follow-up modified HAQ (mHAQ as a continuous variable).
- Change from baseline to 6 month follow-up HAQ (HAQ as a continuous variable).
- Change from baseline to 6 month follow-up modified Disease activity Score (mDAS as a continuous variable).
- Change from baseline to 6 month follow-up Disease activity score- erythrocyte sedimentation rate (DAS ESR) (as a continuous variable).
- Change from baseline to 6 month follow-up DAS- C- reactive protein (DAS CRP) (as a continuous variable).
- Change from baseline to 6 month follow-up patient pain (as a continuous variable).

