9.5. Study Size

Power calculations (below) indicate that to detect a reasonable difference of 15% in the percentage meeting MCID in CDAI, about 300-500 patients per group would be needed.

With the following assumptions:

- Consider the dichotomous outcome of meeting MCID in CDAI.
- We would like to have 90% power to detect a difference between the 2 groups in percentage meeting MCID in CDAI.
- We would like to have a low chance (alpha of 5%) of declaring that there is a difference in the outcomes between the 2 groups when in actuality there is not (type I error).

The following Table 1, gives the number needed per group and total number needed for different scenarios of meeting MCID for CDAI and percent of patients who are available under common support (eg, percent of patients in the control group that are similar enough to the treatment group so that we are comfortable that the 2 cohorts are similar). If we assume that the percentage meeting MCID in CDAI is 50%, the following sample sizes are required.

Table 1. Sample Size Determination

Difference between the 2 groups in percentage meeting MCID in CDAI that can be detected	Analyzable Data Set, N per group	% under common support	N per group required to recruit	Total N required to recruit
10%	535	50%	1070	2140
10%	535	75%	713	1426
15%	237	50%	474	948
15%	237	75%	316	632
20%	131	50%	262	524
20%	131	75%	175	350
25%	84	50%	168	336
25%	84	75%	112	224

Under different scenarios for projections of the total number of tofacitinib 11 mg QD initiators over time, it was estimated that there would be about 180-220 tofacitinib 11 mg QD initiators with 6 month follow-up visits by the end of 2018.

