Based on factors in **Table 1** that differ between the two groups (e.g. standardized difference > 0.1) and clinical input on a priori factors to include, a propensity score will be estimated for propensity of being in the 11 mg QD group. A small number of factors will be considered in the propensity score model; these may include age, gender, disease activity, line of therapy, etc. The primary purpose of the propensity score approach is to determine the patients with “common support” – those patients falling in an overlapping distribution of the propensity score. Patients falling outside the common support would have no comparable patients in the other group and would not be able to be used for comparative analyses.

Here we describe the propensity score matching approach.

***Propensity Score Matching Approach:*** To balance differences in baseline patient and disease characteristics among the 5 mg BID and 11 mg QD groups, we will use matched propensity scores.

***Logistic regression model approach to obtain propensity scores:*** We will use the logistic regression approach (outcome is 11 mg QD therapy) including variables such as the following covariates: age (continuous), gender (male is reference group), baseline CDAI (continuous), line of therapy (categorical), duration of disease (categorical), as appropriate. As mentioned above, we plan to examine all the Table 1 variables, but expect that only a select group will be considered in the propensity score model. The resulting logit model will be of the form:

$$\ln\left(\frac{p}{1-p}\right) = m_{11mgQD}$$

$$= \beta_0 + \beta_1 * age + \beta_2 * gender + \beta_3 * CDAI + \beta_4 * line\ of\ therapy + \dots$$

where  $p$  is the probability of 11mg QD Tofacitinib therapy.

A patient's resulting propensity score from the model is the patients predicted 11 mg QD Tofacitinib ( $p_{11mgQD}$ ), given by

$$p_{11mgQD} = \frac{e^{m_{11mgQD}}}{1 + e^{m_{11mgQD}}}$$

After the propensity score model is fit, **Table 1** will again be constructed with this propensity score matched sample and presented in **Table 1a** to ensure that there are no longer any statistically significant differences between the two groups (11 mg QD and 5 mg BID therapy). For the propensity score matching, it is proposed that a caliper of 0.01 will be used, but the caliper may be increased if the resulting sample size available from the propensity score matching is prohibitive.

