In this second look with adjusted models, we propose to consider covariates with standardized differences > 0.2 as well as age, gender, CDAI and duration of RA (e.g. gender, age, duration of RA, current statin use, prior cDMARD use, prior non-TNF use, current concomitant therapy, CDAI and EQ-5D) in adjusted models. When considering change in outcome, we will also include the baseline level of that covariate in the model (e.g. for change in CDAI, consider baseline CDAI). For the continuous outcomes, mean differences within subject adjusted for covariates will be assessed using linear regression models (least squares means and 95% CIs). For binary outcomes, we will consider multivariable logistic regression models (ORs and 95% CIs). For the primary outcome, the adjusted OR (95% CI) will give the odds of having MCID improvement in the 11 mg QD initiator group as compared to the odds in the 5 mg BID initiator group after adjusting for covariates; the 5 mg BID initiator group will be the reference group. The interpretation will be similar for the other binary secondary outcomes. Please refer to **Table 2\_adj** for the primary outcome and **Table 3\_adj** for the secondary outcomes.

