### **Interim Look:**

Oftentimes when designing a study, investigators would like to get an initial look at the data in order to inform future decisions. While it is not possible to continually re-analyze the data, it is possible to do pre-planned interim looks at the data prior to when there are sufficient patients as per the power calculation. There are however drawbacks to looking at the data prematurely. There is the possibility that incorrect inferences are drawn due to the limited information. This is particularly an issue if the patients accrued at the beginning of the study are somehow different from later patients. Also, when computing the final outcome of the study, it is necessary to adjust for the fact that you have already taken a look at the data. This means that if you are considering that a p-value less than 0.05 would indicate a difference between the two groups, then if you have already taken a look, the p-value required to say that there is a difference between the two groups would need to be less than 0.05.

We are now proposing to consider two interim looks at the data – one at 33% accrual and another at 50% accrual. If we assume that we wish to detect a change in 15% from the proposed MCID of CDAI of 50% with 75% under common support, we would need 237/group analyzable and the p-value for the first interim look would need to be less than 0.001 to be considered statistically significant, a p-value for the second interim look would need to be less than 0.003 to be considered statistically significant and a p-value for the final look would need to be less than 0.049 to be considered statistically significant.

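### Site appears in no visible table or model, so site practice can confound the QD–BID comparison, and standard errors may be too small by an unknown amount

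*Protocol*

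**What the plan says.** Protocol 9.4 describes the source of the patients: "Patients are recruited from 187 private and academic sites across 43 states, with 799 providers participating". Protocol 9.1 states that "patient therapeutic strategies are not determined by this protocol", so formulation follows routine care. On outcomes, Protocol 9.3 says "The endpoints chosen for this study will be extracted from patient and physician questionnaires", and 9.4 adds "Providers and subjects complete study questionnaires approximately every 6 months at routine clinic encounters".

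Under Analysis for Overall Aim, the SAP gives these propensity score covariates: "age (continuous), gender (male is reference group), baseline CDAI (continuous), line of therapy (categorical), duration of disease (categorical), as appropriate". Table 1 covers demographics, comorbidity, treatment history, disease activity and line of therapy. It has no row for site, provider, practice type or region. For the second look the SAP says "For binary outcomes, we will consider multivariable logistic regression models (ORs and 95% CIs", with linear regression for continuous outcomes. It lists nine example covariates, and site is not among them.

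The tests are a t test in Table 2, chi-squared tests in Table 2a and for the binary rows of Table 3, t tests for the continuous rows of Table 3, and ordinary logistic or linear regression in Tables 2_adj and 3_adj. The addendum repeats these on the full and the trimmed populations, again without site. No visible text mentions a random effect, estimating equations, cluster-robust variance or stratification by site.

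Protocol 9.8 describes data review and queries site by site, so the registry knows the site of each record. Protocol 9.9 admits residual confounding in general terms but does not name site.

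**The concern.** Two separate problems can arise.

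- **Confounding.** Sites may differ in how often they use 11 mg QD, in how well their patients respond and in how they score. If these are related, the treatment contrast partly compares sites.
- **Precision.** Even without such a relation, if both outcome and formulation cluster by site, an analysis that treats patients as independent gives standard errors that are too small.

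The SAP's stated purpose is to make the two groups alike before comparing outcomes. It cannot check or balance a factor that it never tabulates. The study hypothesis is similarity, so a bias in either direction could create a difference or hide one. Protocol section 12 says the results may go to the EMA.

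**Working it through.** **1. The plan's own figure.** Inputs from Protocol 9.5: response 50%, difference 15 points, power 90%, and for the error rate "We would like to have a low chance (alpha of 5%) of declaring that there is a difference in the outcomes" (taken as two-sided). With p1 = 0.50, p2 = 0.65 and mean 0.575:

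n = [1.960 × √(2 × 0.575 × 0.425) + 1.282 × √(0.25 + 0.2275)]² / 0.15² ≈ 227

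With the continuity correction this becomes 240, against the plan's 237. The formula treats patients as independent, and the common-support columns only divide by 0.50 or 0.75. No allowance for site is built in.

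**2. Patients per site.** The addendum gives 450 patients (297 QD, 153 BID). The later proposal gives 573 (401 QD, 172 BID). If all registry sites contribute, 450/187 = 2.4 and 573/187 = 3.1 per site. The number of sites that contribute tofacitinib initiators is not given.

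**3. Precision, by formula.** Formulation can vary within a site, so the design effect needs clustering of both variables:

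DEFF = 1 + (m − 1) × ICC(outcome) × ICC(formulation), with intervals wider by √DEFF

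Here m is patients per site; with uneven sites (assumed coefficient of variation 1) the mean is doubled. The assumed ranges are outcome ICC 0.01–0.10 and formulation ICC 0–0.5. The table takes the upper ends (0.10 × 0.5 = 0.05). Power is for 15 points.

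| N | Sites | m | DEFF | Interval wider by | Power |
|---|---|---|---|---|---|
| 450 | 187, equal | 2.4 | 1.07 | 3.5% | 0.843 (from 0.867) |
| 450 | 50, equal | 9 | 1.40 | 18% | 0.738 |
| 450 | 50, uneven | 18 | 1.85 | 36% | 0.618 |
| 573 | 100, equal | 5.7 | 1.24 | 11% | 0.855 (from 0.918) |
| 573 | 50, equal | 11.5 | 1.52 | 23% | 0.777 |

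If formulation ICC is 0, DEFF is 1 in every row.

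**4. Precision, by simulation.** The comparison is unadjusted, with no true difference and a nominal 5% error rate. The SAP's last look is almost the same: "a p-value for the final look would need to be less than 0.049 to be considered statistically significant".

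- Formulation unrelated to site: 4.8–5.8% at N = 450 and 5.1% at N = 573.
- 187 sites, formulation clustered by site: 5.1–6.2% across both sample sizes.
- 60 sites, N = 573, site preference SD 2 on the log-odds scale: 7.5–9.2% at ICC 0.05 and 9.6–11.6% at ICC 0.10, the spread reflecting response rate and site-size assumptions.
- 100 sites, N = 573, ICC 0.05, preference SD 2: 7.2%.
- 50 uneven sites, N = 450, formulation ICC 0.5: 8.0–9.5%.

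**5. Confounding, by simulation.** Site preference is now given an assumed correlation of 0.3 with site response level.

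- N = 450: bias 2.2–4.9 points, error rate 7.5–21.6%. With 187 sites alone the bias is 2.3–4.9 points.
- N = 573: bias 2.5–5.0 points, error rate 9–26%. With 187 sites alone the bias is 2.5–3.8 points and the error rate 9–14%.

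A hand check at 50% response: SE = √(0.25/401 + 0.25/172) = 4.56 points. A bias of 2.5 points is 2.5/4.56 = 0.55 SE, which gives P(Z > 1.41) + P(Z < −2.51) = 0.085. A bias of 3.8 points is 0.83 SE and gives about 0.13. Both agree with the 187-site runs.

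**6. What each remedy does to the bias.** Clustered standard errors leave the estimate unchanged. A random intercept reduced the bias from 5.0 to 2.6 points with 60 sites and from 2.5 to 2.1 with 187. A within-site comparison removed it, with larger standard errors.

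**The case against.** A reader might infer that the confidence intervals are likely too narrow. The documents do not support that. Narrowing needs formulation as well as outcome to cluster by site, and with the only site count given (187) it is negligible. Error rates of roughly 7–12% need few contributing sites and strong preferences, neither of which is documented. Matched Table 2 has no confidence interval at all; there the issue is the p-value. The matched sample is also smaller: if matching is 1:1 (an assumption), at most 2 × 172 = 344 patients remain, or 344/187 = 1.8 per registry site. A proxy run of that size with 60 sites, ICC 0.05 and preference SD 2 gave 6.3%. All of this stands.

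A reader might also infer that the provider chooses the formulation and then scores the CDAI unblinded. The protocol says only that it does not determine treatment, and that endpoints come from patients as well as physicians. Provider choice and open assessment are reasonable inferences from routine care, not stated facts.

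The outcome is change from initiation, and baseline CDAI is in the models, so a stable tendency to score high or low partly cancels. This stands in part: it does not remove site differences in true response, or in scoring that shifts after treatment starts.

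Finally, the covariate lists are open-ended and some text is redacted, so the absence of site can be asserted only for visible text. The general sentence in Protocol 9.9 does not answer the point, because it concerns unmeasured factors and the registry does record site.

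**Conclusion.** The point holds in a limited form. Site is missing from the visible tables, propensity models and outcome models, and no described test allows for clustering.

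Confounding is the larger risk: about 2–5 points of bias at an assumed correlation of 0.3, against a 15-point design difference. It does not vanish when patients are spread over many sites. The documents do not show that such a correlation exists.

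The precision problem is smaller. The p-values in Tables 2 and 3, the standard errors in Table 3 and the intervals in Tables 2_adj and 3_adj may be too small or too narrow by an unknown amount. It matters only if few sites contribute and their preferences are strong.

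Every size given rests on assumed ICCs, contributing-site counts and preference spread, and the simulations are of unadjusted comparisons. Counts of sites by formulation would settle much of the question.

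**What to change.** 1. Add to Tables 1 and 1a the number of sites contributing to each arm and the share of patients from sites that used both formulations.
2. Use site-clustered robust standard errors for Tables 2, 3, 2_adj and 3_adj.
3. As sensitivity analyses of the primary outcome, fit a random intercept for site and a within-site comparison, for example logistic regression conditional on site. The second is needed because clustered standard errors do not remove site confounding and a random intercept does so only in part. Conditioning on site also avoids up to 186 site indicators (187 − 1), which could not fit the second look's limit of 10 covariates.

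The cost is a few table rows, a coded site identifier in the analysis file, and options available in the SAS and Stata versions already named. Intervals may widen slightly. The within-site analysis loses precision because only sites with both formulations, and with both responders and non-responders, contribute to it.

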9.5. Study Size

Power calculations (below) indicate that to detect a reasonable difference of 15% in the percentage meeting MCID in CDAI, about 300-500 patients per group would be needed.

With the following assumptions:

- Consider the dichotomous outcome of meeting MCID in CDAI.
- We would like to have 90% power to detect a difference between the 2 groups in percentage meeting MCID in CDAI.
- We would like to have a low chance (alpha of 5%) of declaring that there is a difference in the outcomes between the 2 groups when in actuality there is not (type I error).

The following Table 1, gives the number needed per group and total number needed for different scenarios of meeting MCID for CDAI and percent of patients who are available under common support (eg, percent of patients in the control group that are similar enough to the treatment group so that we are comfortable that the 2 cohorts are similar). If we assume that the percentage meeting MCID in CDAI is 50%, the following sample sizes are required.

Table 1. Sample Size Determination

Difference between the 2 groups in percentage meeting MCID in CDAI that can be detected	Analyzable Data Set, N per group	% under common support	N per group required to recruit	Total N required to recruit
10%	535	50%	1070	2140
10%	535	75%	713	1426
15%	237	50%	474	948
15%	237	75%	316	632
20%	131	50%	262	524
20%	131	75%	175	350
25%	84	50%	168	336
25%	84	75%	112	224

Under different scenarios for projections of the total number of tofacitinib 11 mg QD initiators over time, it was estimated that there would be about 180-220 tofacitinib 11 mg QD initiators with 6 month follow-up visits by the end of 2018.

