### Secondary Outcomes for Overall Aim:

- Change from baseline to 6 month follow-up CDAI (as a continuous variable)
- Achievement of Remission (CDAI $\leq$ 2.8) at 6 month follow-up (among all)
- Achievement of Remission (CDAI $\leq$ 2.8) at 6 month follow-up (among those that were not in remission at initiation)
- Achievement of Low Disease Activity (LDA) (CDAI $\leq$ 10) at 6 month follow-up (among all)
- Achievement of Low Disease Activity (LDA) (CDAI $\leq$ 10) at 6 month follow-up (among those that were not in remission or LDA at initiation)
- Achievement of improvement from baseline to 6 month follow-up in modified HAQ (mHAQ) of 0.25 (as a dichotomous variable)
- Change from baseline to 6 month follow-up modified HAQ (mHAQ as a continuous variable)
- Achievement of improvement from baseline to 6 month follow-up in HAQ of 0.22 (as a dichotomous variable)
- Change from baseline to 6 month follow-up HAQ (HAQ as a continuous variable)
- Change from baseline to 6 month follow-up modified DAS (mDAS as a continuous variable)
- Change from baseline to 6 month follow-up DAS ESR (as a continuous variable)
- Change from baseline to 6 month follow-up DAS CRP (as a continuous variable)
- Change from baseline to 6 month follow-up patient pain (as a continuous variable)
- Change from baseline to 6 month follow-up patient fatigue (as a continuous variable)
- Change from baseline to 6 month follow-up EQ-5D index (as a continuous variable)

- Modified ACR20, ACR50, ACR70

Please see Appendix for more details on the secondary outcomes.

Patients that switched to an agent other than tofa during the 6 months of follow-up will be considered for the continuous outcomes at the time of switch (rather than at 6 months).

In **Tables 2 and 3**, for the dichotomous primary and secondary outcomes, patients that discontinued or switched to an agent other than tofa will be considered as non-responders (e.g. did not achieve remission for patients that discontinued or switched prior to their 6 month visit).

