### Population for Overall Aim:

For the primary analysis comparing QD to BID patients, we will consider those patients who initiated tofa 5 mg BID on or after February 2016 and those that initiated tofa 11 mg QD after it became available in February 2016. Although the sample size will be smaller than if we consider all tofa 5 mg BID patients, the addition of those patients may introduce noise since there is the possibility that they could differ from the more recent initiators. Therefore, we will consider the cleaner cohort of all patients initiating tofa on or after February 2016.

In order to adequately measure the outcome, the initiators will also be required to have a follow-up visit at 6 months (+/- 3 months) after tofacitinib initiation.

The data cut to be used will be the most recent available.

With regards to dosing, patients can be categorized as follows:

QD dosing: once-daily tofacitinib 11mg

BID dosing: 5mg twice-daily

Other: other dosages including 10 mg and will also include not specified

Those in the "other" category will not be considered in these analyses.

The first initial look at the data has indicated that the tofa 5 mg BID group differs on some characteristics from the tofa 11 mg QD group. To account for these differences, in a second look at the data, we propose to consider models adjusted for no more than 10 covariates. This will provide a robust analysis, while preserving sample size. The full propensity score analysis will be done in the final look at the data when the sample size is large enough (as per preliminary power calculations on page 23).

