**Table 1 continued**

At time of Tofacitinib initiation	11 mg QD N=	5 mg BID N=	Standardized difference
Line of therapy			
1 st			
2 nd			
3 rd			
4 th			

SD = Standard Deviation

IQR = Interquartile Range: 25th percentile, 75th percentile

Standardized differences rather than p-values can be more informative regarding the actual size of the difference between the two groups; hence, it is suggested that they be used rather than p-values to inform which variables are to be included in the propensity score model.

\*The scale ranges from 0-100 with 0 being fatigue is no problem to 100 fatigue is a major problem.

**Table 1a. Patient Demographic and Clinical Characteristics for Tofacitinib Initiators by Dose (5 mg BID and 11 mg QD) after Propensity Score Matching.**

Repeat Table 1 in the Propensity Score Matched cohort. *Table only generated for the final analysis.*

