**Table 2: Primary outcome of 11 mg QD vs. 5 mg BID Initiators**

*Table generated “after propensity score matching” only for the final analysis.*

	11 mg QD Initiators N=	5 mg BID Initiators N=	p-value*
Primary Outcome	Response Rate	Response Rate	
MCID Improvement in difference in CDAI from initiation to 6 month visit			

\*The p-value will be reported from the t test of the mean difference between the 11 mg QD and 5 mg BID initiators according to the primary outcome.

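### The study size section promises 90% power for a 15-point difference but never counts the smaller 5 mg BID group, which falls short of that target at every documented count

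*Protocol*

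**What the plan says.** Protocol 9.5 and the SAP power appendix share one calculation. The aim is put as "We would like to have 90% power to detect a difference between the 2 groups in percentage meeting MCID in CDAI", and the headline is that "to detect a reasonable difference of 15% in the percentage meeting MCID in CDAI, about 300-500 patients per group would be needed". Table 1 gives 237 analysable per group for 15 points from a 50% response rate. Dividing by common support gives 316 (75%) or 474 (50%) per group before matching. The Interim Look section of the SAP repeats 237 per group with 75% support and sets the final significance level at 0.049.

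The only accrual forecast in the protocol is for one group: "it was estimated that there would be about 180-220 tofacitinib 11 mg QD initiators with 6 month follow-up visits by the end of 2018". The SAP's Preliminary Projections extend it to 260-320 by the end of 2019, again for QD only. No BID forecast is visible.

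Protocol 9.7 makes a propensity-score-matched subset the basis of the final analyses. The SAP, under Population for Overall Aim, ties this to the power calculation: "The full propensity score analysis will be done in the final look at the data when the sample size is large enough". For matching, "it is proposed that a caliper of 0.01 will be used", with room to widen it.

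The BID counts appear only in the SAP addenda: 153 eligible of 258 initiators at the September 2018 cut, and 172 with an eligible six-month visit at the August 2019 cut, before the valid-CDAI check.

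**The concern.** The study size section describes the larger group and omits the one that limits the comparison. By its own milestones the protocol was written retrospectively and finalised in December 2019, after both data cuts. Its data source section quotes September 2019 registry totals. Section 9.5 still gives only the 15-point target and a QD forecast for the end of 2018.

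The SAP's condition of a large enough sample also appears not to have been met. Addendum 054c describes Table 1a, the matched baseline table, in the past tense, and the SAP says of that table "Table only generated for the final analysis". Matching therefore seems to have been run on 297 QD and 153 BID patients, both below 316.

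What is at stake is the reading of a null result. The stated hypothesis is that the two formulations perform similarly. A non-significant p-value printed beside a 90%-power, 15-point design statement invites the conclusion that 15 points has been excluded. SAP Table 2 shows two response rates and a p-value from a "t test of the mean difference between the 11 mg QD and 5 mg BID initiators according to the primary outcome". Table 2_adj gives an odds ratio with its CI. Neither shows a risk difference with an interval.

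**Working it through.** **Reproducing the plan's figure.** Inputs from Protocol 9.5: 50% versus 65%, alpha 5% (taken as two-sided), power 90%.

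- Unpooled: n = (1.960 + 1.282)² × (0.25 + 0.2275) / 0.15² = 223.0.
- With continuity correction, n/4 × [1 + √(1 + 4/(n × 0.15))]² = 236.1, against 237 stated.
- The same formula gives 534.7 and 130.6 for the 10- and 20-point rows (535 and 131 stated). It gives 81.4 for the 25-point row (84 stated).
- The pooled version with correction gives 538, 240, 134 and 85, all within 3% of the table.
- 237/0.75 = 316 and 237/0.50 = 474, exactly as printed.

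The table is sound for equal groups.

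**BID counts against the table's pre-matching column.** The widened-window count is derived: 172 + 36 patients seen in the first year but without a six-month visit = 208. For QD, 401 + 80 = 481, and 481 + 208 = 689, the total the SAP states.

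| BID count | Rows met |
|---|---|
| 153 | 25 points at 75% (112) |
| 172 | 25 points at 75% and 50% (112, 168) |
| 208 or 258 | those two, plus 20 points at 75% (175) |

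None meets 316 or 474.

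**Power for 15 points, assuming 1:1 matching.** With p̄ = 0.575 and two-sided alpha 0.049 (z = 1.969):

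power = Φ{[0.15 − z√(2p̄(1−p̄)/n)] / √[(0.25 + 0.2275)/n]}

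For n = 153: (0.15 − 1.969 × 0.0565)/0.0559 = 0.693, so power is 0.756. For n = 172: (0.15 − 1.969 × 0.0533)/0.0527 = 0.855, so power is 0.804. The planned 237 gives 0.912 by this formula, which has no continuity correction.

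| BID available | No matching loss | 75% support | 50% support |
|---|---|---|---|
| 153 | 76% (153 pairs) | 63% (115) | 46% (76) |
| 172 | 80% (172) | 68% (129) | 51% (86) |
| 208 (wider window) | 87% (208) | 76% (156) | 59% (104) |

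Difference detectable with 90% power, from 50% upwards: 18.1, 20.8 and 25.2 points with 153 BID; 17.2, 19.7 and 23.8 points with 172. For a lower-group rate between 30% and 50%, the no-loss power stays at 75-77% (153) and 80-82% (172).

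**Other ratios, same alpha.**

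- 1:2 with 172 BID: about 90% with no loss, 80-81% at 75% support, 63-64% at 50%.
- 297 QD to 153 BID (just short of 1:2, and also the whole unmatched sample): about 86%.
- 1:2 in the widened window: 95%, 87% and 71-72%.
- Unmatched: 92% (401 vs 172) and 96% (481 vs 208), before adjustment.

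**Precision.** The 95% CI half-width for the risk difference is 1.96√(2p(1−p)/n). At p = 0.50 it is 11.2 points (153 pairs), 12.9 (115) and 15.9 (76). At p = 0.30 it is 10.3, 11.8 and 14.6. A rate below 50% is possible because, for the dichotomous outcomes, "patients that discontinued or switched to an agent other than tofa will be considered as non-responders".

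**The case against.** The strongest reply is that an a priori calculation is not made wrong by later accrual, and the table itself is correct. Part of the gap is also visible: 180-220 projected QD patients sit beside a need for 300-500 per group, and Table 1 lists 20- and 25-point rows. That is fair, but the text never says which row the BID numbers support, and the protocol post-dates the counts.

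The lower power figures are scenarios. They need 1:1 matching and loss of a quarter or half of the BID patients. BID would be matched from a QD pool about twice its size, so the table's support percentages may not carry over. The matching ratio, or a BID forecast, could lie in redacted text. This stands, and it is why the figures are conditional. The no-loss 1:1 figures of 76% and 80% need no assumption about support.

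The 258 initiators exceed 237 and fail only the pre-matching figures; 237/258 = 92% would have to be matched. But 258 includes patients with no six-month visit. It applies only to the sensitivity analysis that counts them as non-responders, where crude power at 611 vs 258 would be about 98% if the rates stayed at 50% and 65%.

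The unmatched analyses come close to 90% or exceed it. That also stands, so the point must not be widened to every analysis. The full-population analysis is, however, labelled exploratory.

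Finally, the addenda cite a non-inferiority margin guideline and mention an NI table whose content is redacted. It may already report a difference with a CI, which would meet the second part of the fix.

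**Conclusion.** The concern holds and should be fixed. The stated design of 90% power for 15 points cannot be shown to apply to the matched final analysis. In the 3-9 month window, only a 1:2 match of the 172 BID patients with almost no loss would reach it.

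Under 1:1 matching in that window, a true 15-point difference would be missed at least 20-24% of the time, 32-37% at 75% support and 49-54% at 50%. The plan states 10% (about 9% by the formula used here). These figures rest on the plan's own 50% versus 65%, alpha 0.049, independent groups, and BID counts taken before any loss to the valid-CDAI check at the second cut. They do not use the observed effect. The shortfall of every BID count against 316 and 474 rests on no such assumption.

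**What to change.** 1. Leave the planning calculation and Table 1 as the record. Beside them, in Protocol 9.5 and the SAP power appendix, say that 5 mg BID is the limiting group, give the matching ratio, and give power and detectable difference at the BID-limited matched size. Label these as conditional on ratio, visit window and common support. For 1:1 in the 3-9 month window, the entries are at most 76% (153 pairs) or 80% (172 pairs), 63-68% at 75% support and 46-51% at 50%, with detectable differences of about 17-18, 20-21 and 24-25 points.
2. Add the risk difference with its 95% CI for the matched sample to SAP Table 2, unless the redacted non-inferiority table already reports it for that sample.

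The cost is one short paragraph in each document and at most one table column. It needs no new patients and no change to the primary analysis. The drawback is that the stated power becomes less favourable.
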